## 4 STUDY POPULATION

### 4.1 NUMBER OF PARTICIPANTS

**WP1:** >100,000 infants born in the UK with gestational age (GA) <32 weeks between 01/01/2008 & 31/12/2019 (National Neonatal Research Database, NNRD).

**WP2:** 300 mother-infant dyads: 200 preterm deliveries with GA <32 weeks (exposed, cases); 100 term deliveries with GA >37 weeks (non-exposed, comparators).

**WP3:** 300 children (200 preterm, 100 comparators).

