**WP3.** There are no prior fMRI studies of young children born preterm (2-6 years) from which to estimate the size of the effect of preterm birth on aspects of their functional brain responses. Given this, we performed an indicative power analysis to determine the sensitivity to detect individual differences in two measures of social brain development in 3- to 5-year-olds (n=65). In this sample, the effect size of age on inter-region correlations among social brain regions, controlling for participant motion, was  $r_s(62)=.48$ ,  $p=7.1 \times 10^{-5}$ , and the effect size of age on the functional maturity of this cortical network, controlling for motion, was  $r_s(62)=.40$ ,  $p=.001$ . These are medium-large effects. Sensitivity analyses with n=246 children and 90% power could detect effects larger than  $r=.20$ . The sample will enable subset analyses based on PTB-RFs identified in WP1. An indicative power estimate for subset analyses based on effect size of age between 3 and 5 years and assuming  $\alpha = .05$  and 90% power, is that fMRI data from n=42 or n=60 children, respectively, would detect the two effects above.

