**WP3.** fMRI data will be pre-processed using fMRIPrep. A general-linear model will be used to analyse BOLD activity of each participant. Individual functional regions of interest (ROIs) will be defined as the 80 voxels within targeted search spaces (for social, attention, and language networks) that have the highest contrast values (i.e., are most similar to the adult timecourse), using a split-half approach such that extraction of response time courses and ROI definition occur in independent data. Functional maturity of each ROI will be calculated as the correlation between each child's (split-half) timecourse and the average adult timecourse; inter-region correlations will be calculated as the average correlation between timecourses across ROIs within each network. These measures capture region-specific functional maturity and the functional coherence of each network. To ensure unpredicted effects do not go undetected in such a valuable dataset, additional measures of brain development, including the response magnitude to domain-relevant scenes will be explored. Whole-brain random effects analyses will be conducted to identify any regions that are differentially recruited during domain-relevant scenes

relative to control scenes in preterm children as compared to term-born children. We will explore the impact of preterm birth on response time courses for attention and language, as well as social networks. These analyses will be corrected for multiple comparisons by estimating the false-positive rate via 5,000 Monte Carlo permutations.

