Diffusion images will be pre-processed (realigned, co-registered to the anatomical, and normalised) to reduce distortion, and submitted to eddy-current and motion correction analyses using QSIprep. Diffusion data will be analysed with a tensor model. Tensor model metrics (fractional anisotropy [FA] and mean diffusivity [MD]) are well studied and can be interpreted within a large literature on white matter development. Specific tracts will be identified based on previous work on white matter development and particular cognitive functions (for example, for social cognition, we will focus on the arcuate fasciculus, inferior fronto-occipital fasciculus, and corpus callosum). Average FA and MD will be calculated within tracts that connect individually-defined functional ROIs (as defined above), per network. Additionally, metrics with increased biological specificity from more advanced biophysical models of the diffusion signal will be explored. For example, the NODDI model enables calculating the intracellular volume fraction of water (ICVF) and orientation dispersion index (ODI).

Structural images will be used as anatomical reference for the diffusion and fMRI data. Structural images will be processed using FreeSurfer performing cortical reconstruction and volumetric segmentation. This step will be run inside the QSIprep and fMRIPrep processes.

Linear and mixed effects regressions will be used. Analyses with neuroimaging measures will include participant motion and age as covariates. When multiple statistical tests within a family are conducted, Bonferroni corrections will be applied.

In neuroimaging analyses, we will control type 1 error while minimising the risk of type 2 error by use of family-wise error rate and threshold-free cluster enhancement.

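### WP3 names tracts a priori but averages FA and MD in tracts tied to each child's own fMRI regions; the two rules are not reconciled, and a child without usable fMRI gets no score

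*Protocol*

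**What the plan says.** The WP3 part of protocol section 9.2 locates the diffusion measure in two consecutive steps.

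- Tract choice: "Specific tracts will be identified based on previous work on white matter development and particular cognitive functions". For social cognition the examples are the arcuate fasciculus, the inferior fronto-occipital fasciculus and the corpus callosum.
- Where the values are averaged: "Average FA and MD will be calculated within tracts that connect individually-defined functional ROIs (as defined above), per network".

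The regions in the second step are defined earlier in 9.2 from each child's fMRI: "Individual functional regions of interest (ROIs) will be defined as the 80 voxels within targeted search spaces", namely the voxels "that have the highest contrast values (i.e., are most similar to the adult timecourse". Region definition and the functional score are kept apart, "using a split-half approach such that extraction of response time courses and ROI definition occur in independent data". Neuroimaging models carry participant motion and age as covariates, and Bonferroni correction applies within a family of tests.

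On numbers, section 4.1 gives "300 children (200 preterm, 100 comparators" for WP3. Section 9.1 gives "Sensitivity analyses with n=246 children and 90% power could detect effects larger than" a correlation of .20.

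**The concern.** The only sentence that says where FA and MD are averaged requires functional regions, and these exist only if the child's fMRI is usable. The preceding sentence names anatomical tracts that could be segmented without any fMRI, but it does not say whether they can be scored alone or how they combine with the region rule.

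Two consequences follow from the text.

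1. A child with usable diffusion data and unusable fMRI has no FA or MD, and no alternative scoring is stated. Such children are foreseeable. Section 1.2.3 acknowledges the difficulty of fMRI at this age, Table 2 puts structural, diffusion and functional imaging in a 60-minute MRI, and section 10 describes mock-scan training and reminders to keep still. The children most plausibly lost are those who cannot keep still.
2. The white matter averaged can differ between children according to where their regions fall. If placement varies with prematurity or scan quality, a preterm-term difference in FA could partly reflect sampling of different white matter.

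What is at stake is mainly the structural side of hypotheses 3ii and 3iii: the preterm-term comparison, and the prediction of structural maturity at 5 years from the risk factors found in WP1.

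**Working it through.** **1. The two rules side by side (protocol 9.2, WP3)**

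| | A priori tracts | Tracts connecting individual regions |
|---|---|---|
| Source of location | Earlier work on white matter and cognition | The child's own fMRI |
| Needs usable fMRI? | No | Yes |
| Same anatomical target in every child? | Yes | Not necessarily |
| Stated as the place where FA and MD are averaged? | No | Yes |

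The rules can be read jointly, as the named bundles restricted to the part that connects the regions. The regions are still needed on that reading, so the scoring gap remains.

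**2. What the split-half step covers.** It makes region definition independent of the extracted functional time course. FA and MD come from another acquisition, and the step does not stop region placement from deciding which white matter is averaged.

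**3. The plan's own power figures.** Inputs from 9.1: alpha .05, 90% power, n=246, correlations .48 and .40, subset sizes 42 and 60. Sidedness is not stated; two-sided is assumed. With Fisher's z:

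- n = ((1.960 + 1.282) / atanh(r))² + 3. For r=.48 this is 41.4, so 42 (stated 42). For r=.40 it is 61.5, so 62 (stated 60).
- Detectable r = tanh((1.960 + 1.282) / √(n − 3)). For n=246 this is tanh(3.242/15.59) = .205 (stated .20). Power at r=.20 is 88.5%.

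The figures reproduce closely, so there is no arithmetic error here.

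**4. What n=246 counts.** 246/300 = 82%. Section 9.1 does not say whether 246 means children attending, children with usable fMRI, children with usable diffusion data, or children with both. No rate of usable scans is given for either modality, so the number of children affected cannot be derived.

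**5. Illustration only.** Assume 246 children have usable diffusion data and a share f of them also have usable fMRI. A structure-only analysis under the rule as written then has:

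| f (assumed) | n scored | Detectable r, 90% power | Power at r=.20 |
|---|---|---|---|
| 1.0 | 246 | .205 | 88.5% |
| 0.9 | 221 | .216 | 85% |
| 0.8 | 196 | .229 | 80% |
| 0.7 | 172 | .244 | 75% |

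Scoring the named tracts without fMRI would restore the first row for structure-only analyses. It recovers nobody for a structure-function analysis, which needs both scans in each child.

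**The case against.** The strongest reply has four parts.

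- **Deliberate design.** Averaging in tracts that connect functional regions matches the question about networks, and whole named tracts measure something different. This stands, and it is why the individual-region measure should be kept for structure-function questions. The documents do not settle which measure serves those better.
- **Bounded placement.** Regions must lie inside targeted search spaces, and motion is a covariate. Both limit how far placement can matter. Neither scores a child who has no regions, and a motion covariate does not change which white matter was averaged.
- **A matter for the SAP.** Handling of a failed modality is often left there, and the SAP is not at hand. This has force for a missing-data rule alone. But the protocol itself fixes a scoring location and sets it beside a different one without saying how they combine.
- **Small gain.** Children who cannot keep still may lose diffusion data too, so the number recovered could be small or nil. This stands as an uncertainty about size.

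A reader might go further and infer that FA and MD are circular with the functional measure, so that structure-function correlations would be spurious. The documents do not support that. FA and MD come from a separate acquisition, no voxel is selected on FA or MD, the functional score uses data independent of region definition, and no model of FA or MD against functional maturity is written; that link is inferred from hypothesis 3ii. Any induced correlation would depend on an assumed effect of misplacement on both measures, which may be near zero.

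**Conclusion.** The point holds as a low-cost improvement. Section 9.2 gives two locations for the tensor measures without reconciling them. The one used for averaging leaves a child with usable diffusion data but unusable fMRI without FA or MD, and it lets the sampled white matter vary between children. This rests on the text alone.

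Its size is unknown. The power range in the illustration depends wholly on the assumed share f and on taking 246 as the count with usable diffusion data. A reader might subtract 246 from 300 and conclude that the difference is the number of good diffusion scans lost to failed fMRI. The protocol does not explain that gap. It could be attendance, in which case the loss specific to failed fMRI could be nil. Nor can the size or direction of any bias from region placement be derived. FA and MD are also not designated as the single structural endpoint of WP3; section 2.2.3 speaks only of structural and functional substrates in general.

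**What to change.** In section 9.2 (WP3), state that:

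1. For structure-only analyses (preterm versus term, and WP1 risk factors predicting structural maturity), FA and MD are scored in the named a priori tracts for each network, segmented from diffusion and structural data alone, in every child with usable diffusion data, whether or not fMRI succeeded.
2. For structure-function analyses, FA and MD in tracts connecting individual functional regions are kept, in children with both scans, and those results are checked against the a priori tract measure.

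In section 9.1, say which children n=246 counts.

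The cost is wording, one extra tract segmentation on scans already planned, and a few more tests within the Bonferroni family. The price in content is a structural measure less tailored to each child's functional anatomy for the structure-only questions. Nothing changes for participants.

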# 1 INTRODUCTION

## 1.1 BACKGROUND

Globally, preterm birth (PTB), defined as birth at less than 37 weeks of gestation, affects 15 million pregnancies per annum, with country prevalence between 5 and 18%. Over the past two decades, the survival rate of children born preterm has improved due to advances in perinatal medicine but outcomes remain challenging: 10-15% of children born very preterm (<32 weeks) develop cerebral palsy, 30-50% develop an intellectual disability, and this population is at increased risk of problems with socialisation, behaviour, language, low educational attainment, autism, and attention deficit hyperactivity disorder. Adults who were born preterm are more likely to experience a mood disorder, age-related cognitive impairment, schizophrenia, and cardiometabolic disease. PTB accounts for one of the highest numbers of disability-adjusted life years of any single childhood condition. **There are no effective treatments for improving brain health after preterm birth, which brings into sharp focus the need to identify protective factors and intervention targets.**

The neurobiological basis for adverse neurological, cognitive and psychiatric outcomes following preterm birth is related to cerebral white matter injury and subsequent dysmaturational processes in white matter and neuroaxonal structures collectively termed the ‘encephalopathy of prematurity’ (EoP). With features of EoP apparent on magnetic resonance imaging (MRI), this has become an important assessment modality for investigating determinants of brain health in preterm infants.

**Our premise, based on studies showing that adverse outcomes are not inevitable, is that it is not PTB per se that has a deleterious effect on brain development but rather, it is multiple, often interacting PTB-associated risk factors (PTB-RFs).** These are biological, psychosocial, and social/infrastructural, and can affect parent or child, or be shared, for instance: maternal/infant stress, infection/inflammation, suboptimal infant nutrition, co-morbidities of PTB, and socioeconomic deprivation (Figure 1).

[figure not shown]

Figure 1. PTB-associated risk factors linked with altered cognition in children, proposed biological pathways that transmit risk to atypical brain development/outcome, and image biomarkers for delineating upstream pathways and predicting risk and resilience

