## Hypotheses

Work package 1:

1) Specific preterm birth associated risk factors (PTB-RFs), which may be clinical/demographic, psychosocial (e.g. maternal stress), or social/infrastructural (e.g. deprivation), modify the relationship between GA at birth and neurodevelopmental and/or educational outcomes

Work package 2:

2i) Atypical activation of the HPA axis leads to EoP, indexed on MRI by dysmaturity (altered chronological brain age), reduced connectome complexity, and biomarkers of hypomyelination

2ii) DNAm proxies of chronic systemic inflammation are present in preterm infants at term equivalent age and are associated with MRI features of EoP.

2iii) The effect of PTB-RFs identified in WP1 on brain development are mediated by alterations in the neonatal HPA axis and/or chronic systemic inflammation.

Work package 3:

3i) Preterm children have domain-specific delays in cognition at school age

3ii) Structure-function networks underpinning cognition are altered in preterm children

3iii) PTB-RFs identified in WP1 predict structural and functional maturity at 5-years

This protocol describes a programme of work packages. Permissions and approvals for each work package will be managed separately. New approvals will be sought for WP1 which will be led and managed by investigators based at Imperial College London. New approvals will also be sought for WP2 which will be led and managed by investigators based at the University of Edinburgh. WP3 already has approvals in place and is managed by University of Edinburgh investigators (Research Ethics

Committee No: 16/SS/0154, NHS Lothian R&D No: 2016/0255). Permissions are not required for WP4. Detailed information about these arrangements can be found in section 12.1 Ethical Conduct.

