## 3 STUDY DESIGN

**WP1 is a national population-based cohort study:** >100,000 infants born in the UK with gestational age (GA) <32 weeks between 01/01/2008 & 31/12/2019 (National Neonatal Research Database, NNRD). Records will be linked between three databases: NNRD, National Pupil Database and the ScotXed Pupil Census.

**WP2 is an exposure-based short-term cohort study:** 300 mother-infant dyads (200 preterm with GA <32 weeks [exposed], 100 term with GA >37 weeks [non-exposed comparators]), recruited from the Edinburgh Royal Infirmary. The preterm group will be identified from infants born to women who present with threatened preterm birth and for whom delivery is planned or expected at less than 32 weeks GA. Term controls will be identified from the labour ward or antenatal clinic.

**WP3 is an exposure-based longitudinal cohort study:** 300 children (200 preterm, 100 term) are participants in a long-term cohort study of the effect of preterm birth on brain growth.

**WP4 is a participatory project:** it will engage and involve a parent advisory group (n=6-8) and the Adult Preemie Advocacy Network.

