## 4.2 INCLUSION CRITERIA

**WP1:** All neonates with GA < 32 weeks born in Great Britain and admitted to a neonatal unit. Data are available from England and Wales from 2012, and from Scotland from 2014.

**WP2:** Exposed: 300 preterm infants born at <32 weeks of gestational age (GA). Non-exposed comparators: 100 term infants born at >37 weeks of GA\*.

Preterm infants are included if a mother booked her pregnancy and delivered at Simpson Centre for Reproductive Health (SCRH, the study centre), or if a mother booked her pregnancy at a hospital outside the study centre but was transferred to it with her baby *in utero* due to planned or expected birth <32 weeks. Preterm infants who are transferred to SCRH *ex utero* for intensive care are not included.

\*GA is estimated based on first trimester ultrasound.

**WP3:** 300 participants (200 preterm infants and 100 comparators) in Theirworld Edinburgh Birth Cohort will be invited for MRI and cognitive assessments at age 5 years.

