# 8 DATA MANAGEMENT

## 8.1 Personal Data

**WP1:** The National Neonatal Research Database contains quality-assured data (the Neonatal Data Set, an NHS Information Standard; SCCI1595). Records of infants will be linked using date of birth, postcode and sex. De-identified datasets will be stored and analysed on a secure university system.

**WP2:** Personal data will include name, CHI number of mother and infant, address, email, telephone number, date of birth of infant, ethnicity and health data. Participants will be issued with a unique identifier at the point of recruitment and this shall be used to label all research data including biological samples. Contact data and research data will be stored separately, linked by the unique identifier.

**WP3:** Personal data will include name, CHI number of mother and infant, address, email, telephone number, date of birth of infant, ethnicity and health data. Participants will be issued with a unique identifier at the point of recruitment and this shall be used to label all research data including biological samples. Contact data and research data will be stored separately, linked by the unique identifier.

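### WP3's stated covariates leave the preterm-versus-term contrasts open to confounding by deprivation, so they support a total group difference but not an effect of preterm birth itself

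*Protocol*

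**What the plan says.** The WP3 part of section 9.2 (Protocol) gives one sentence on covariates: "Analyses with neuroimaging measures will include participant motion and age as covariates". No covariates are named for the cognitive scores. The same section plans a whole-brain comparison of regional recruitment "in preterm children as compared to term-born children", and speaks of exploring the impact of preterm birth on response time courses.

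The hypotheses served are 3i, "Preterm children have domain-specific delays in cognition at school age", and 3ii, that structure-function networks underlying cognition are altered in preterm children.

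The comparators come from an existing cohort. Section 3 states that "300 children (200 preterm, 100 term) are participants in a long-term cohort study of the effect of preterm birth on brain growth", and section 4.2 that "300 participants (200 preterm infants and 100 comparators) in Theirworld Edinburgh Birth Cohort will be invited for MRI and cognitive assessments at age 5 years". Neither section says how the term children were chosen or whether they were balanced against the preterm children; both cite a separately published cohort protocol.

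Section 1.1 words its premise as follows: "it is not PTB per se that has a deleterious effect on brain development but rather, it is multiple, often interacting PTB-associated risk factors". Socioeconomic deprivation is one of its examples.

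WP1 treats the same issue explicitly. Its part of section 9.2 models (S)IMD quintile and then adjusts for potential confounders and effect modifiers.

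**The concern.** A variable that is associated with group membership and also affects the outcome biases an unadjusted group contrast as an estimate of the group's own effect. Section 1.1 gives deprivation both properties. The WP3 model, as stated, handles head motion and age but not deprivation, and no design feature described in this document handles it either.

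At stake is what a positive finding would mean. A difference in network maturity or task score could reflect preterm birth, the circumstances that accompany it, or both. The programme's premise is about telling these apart. Hypothesis 3iii, objective 2.1.3 and the subset analyses in section 9.1 examine risk factors as predictors, but no WP3 text enters them into the group contrasts for 3i and 3ii.

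**Working it through.** **1. The plan's own WP3 figures.** Section 9.1 gives r = .20 detectable with n = 246 at 90% power, and n = 42 and n = 60 for correlations of .48 and .40, with alpha .05. Two-sided Fisher z, n = ((1.960 + 1.282)/atanh r)² + 3:

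- r = .48: 41.4, so 42 (stated 42).
- r = .40: 61.5, so 62 (stated 60).
- n = 246: r = tanh(3.242/√243) = .205 (stated .20); power at r = .20 is 88.5%.

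The figures reproduce closely. They concern correlations, chiefly with age, and say nothing about confounding of a group contrast.

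**2. Detectable group difference.** d = 3.242 × √(1/n₁ + 1/n₂).

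- 200 v 100 (sections 3 and 4.1): 3.242 × 0.1225 = 0.40.
- 164 v 82 (an assumption: the 246 of section 9.1 split 2:1): 3.242 × 0.1352 = 0.44.

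**3. Shift from an omitted covariate.** With no effect of preterm birth itself, shift in d = (group gap in deprivation, in SD) × (outcome slope, SD per SD of deprivation). The protocol supplies neither input, so both are assumed: gap 0.2, 0.3 or 0.5; slope 0.1, 0.2 or 0.3.

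**4. Rejection of that null** by one two-sided 5% test, with SE = √(1/n₁ + 1/n₂): Φ(d/SE − 1.96) + Φ(−d/SE − 1.96).

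| Gap | Slope | Shift d | 200 v 100 | 164 v 82 |
|---|---|---|---|---|
| 0.2 | 0.1 | 0.02 | 5.3% | 5.3% |
| 0.2 | 0.2 | 0.04 | 6.2% | 6.0% |
| 0.2 | 0.3 | 0.06 | 7.8% | 7.3% |
| 0.3 | 0.1 | 0.03 | 5.7% | 5.6% |
| 0.3 | 0.2 | 0.06 | 7.8% | 7.3% |
| 0.3 | 0.3 | 0.09 | 11.4% | 10.2% |
| 0.5 | 0.1 | 0.05 | 6.9% | 6.6% |
| 0.5 | 0.2 | 0.10 | 12.9% | 11.5% |
| 0.5 | 0.3 | 0.15 | 23.2% | 19.8% |

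Against the detectable difference, the largest shift is 0.15/0.40 = 38% at 200 v 100, or 0.15/0.44 = 34% at 164 v 82. The smallest is 0.02/0.40 = 5%.

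**5. Limits.** The percentages are for a single test at 5%. Section 9.2 plans Bonferroni, permutation and family-wise corrections, so these rates do not carry over directly. The shift d is not changed by such corrections.

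**The case against.** Four objections deserve weight.

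*The covariate sentence is not exclusive.* Saying that two covariates will be included does not rule out others, and a fuller list could sit in an analysis plan that is not shown. This stands as a caution. Still, the protocol chose to specify the WP3 adjustment and stopped at motion and age, while for WP1 it wrote the confounder adjustment out.

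*The term children may have been matched.* A reader might infer from the silence that the comparators are unmatched. The document does not support that: selection belongs to a cohort whose protocol is cited but not at hand. All that can be said is that no matching is described here.

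*The total contrast may be what WP3 wants.* Hypotheses 3i and 3ii can be read as descriptions of preterm children as a group, and section 1.2 frames preterm birth as a multi-dimensional exposure, which puts deprivation partly inside it. On that reading, detecting a difference that arises through deprivation is not a false positive. This stands, and it is why the unadjusted contrast should be kept. But section 9.2 also speaks of the impact of preterm birth, and WP3 does not say which quantity it targets.

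*Deriving (S)IMD may conflict with data handling.* Section 8.1 keeps contact and research data apart, and section 8.2 restricts the flow of personal data. This does not hold as a barrier: hypothesis 3iii and the subset analyses in section 9.1 already need WP1 risk factors for each child, and (S)IMD is one of WP1's two main independent variables.

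**Conclusion.** The concern holds in a limited form. With motion and age as the only named covariates and no matching described, the WP3 group contrasts support a statement that preterm and term children differ. They do not support attributing that difference to preterm birth itself.

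A reader might go further and infer that any observed difference must mix preterm birth with deprivation, or that the tests have an inflated false-positive rate. The protocol shows neither. It reports no imbalance between the groups, and the inflated rates apply only to a null of no effect net of deprivation, which WP3 does not state. Nor can WP3 be said to ignore risk factors, since hypothesis 3iii studies them as predictors.

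The size is unknown. On the assumed inputs the shift is d = 0.02-0.15: negligible at the low end, over a third of the detectable difference at 200 v 100 at the high end. No stated figure is wrong on this point. It is a worthwhile, inexpensive improvement to the plan.

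**What to change.** In the WP3 part of section 9.2, for each preterm-versus-term comparison under 3i and 3ii (functional, diffusion and structural imaging, and cognitive scores):

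- Keep the model with age (and motion for imaging), and label it the total group contrast.
- Report beside it a model that adds (S)IMD, sex and, where the cohort holds it, parental education. Sex is added as an ordinary baseline covariate; section 1.1 does not name it as a risk factor, and the point does not depend on it.
- Limit statements about an effect of preterm birth itself to what the adjusted model supports.

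(S)IMD can be derived from data already held; section 8.1 says for WP3: "Personal data will include name, CHI number of mother and infant, address, email, telephone number, date of birth of infant, ethnicity and health data". The text should say which address is used, since WP1 takes the postcode at birth.

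The cost is protocol or analysis-plan wording, one extra model per comparison and a few degrees of freedom. The adjusted difference may be smaller. No new participants or assessments are needed, and readers who regard deprivation as part of the exposure still have the total contrast.

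### For WP3 regression families on summary measures, plain Bonferroni is valid, but Holm's step-down rule holds the same family-wise error and never rejects less

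*Protocol*

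**What the plan says.** Protocol section 9.2 (WP3) gives three multiplicity rules.

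- **Whole-brain contrasts and response time courses:** "These analyses will be corrected for multiple comparisons by estimating the false-positive rate via 5,000 Monte Carlo permutations".
- **Families of tests**, stated straight after the choice of linear and mixed-effects regressions with motion and age as covariates: "When multiple statistical tests within a family are conducted, Bonferroni corrections will be applied".
- **Imaging maps:** "In neuroimaging analyses, we will control type 1 error while minimising the risk of type 2 error by use of family-wise error rate", the sentence going on to name threshold-free cluster enhancement.

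The section does not define a family or list its members. The summary measures that could form one are functional maturity and inter-region correlation "for social, attention, and language networks", and average FA and MD per network.

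On power, section 9.1 (WP3) says "Sensitivity analyses with n=246 children and 90% power could detect effects larger than" r=.20. For subset analyses at alpha .05 and 90% power it "is that fMRI data from n=42 or n=60 children, respectively, would detect the two effects above", those effects being .48 and .40. No multiplicity divisor appears in either statement.

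**The concern.** The Bonferroni sentence is an unconditional choice of method. For hypothesis tests there is a procedure that needs no further assumption, has the same family-wise error guarantee, and rejects every hypothesis that Bonferroni rejects and sometimes more. Fixing the weaker procedure gives up power whenever two or more effects in a family are real.

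WP3 draws on 300 children already enrolled in an existing cohort (sections 3, 4.2 and 5.1), so lost power cannot readily be made good by recruiting. The WP3 endpoint also asks whether atypicalities are domain-specific or domain-general, so finding all the real effects in a family matters as well as finding one.

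**Working it through.** **Inputs.** From section 9.1: n=246, r=.20, power 90%, alpha .05. Sidedness is not stated; two-sided is assumed because it comes close to the stated figures and one-sided does not (one-sided gives n=35 and n=51, and 93.5% power). Assumptions not in the protocol: families of m=3 (three networks) or m=6 (three networks by two measures), equal effects of r=.20, and a correlation of .5 between test statistics.

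**Step 1: the protocol's own figures.** With Fisher's z, n = ((1.960 + 1.282)/atanh r)² + 3.

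- r=.48: (3.242/.523)² + 3 = 41.4, so 42 (stated 42).
- r=.40: (3.242/.424)² + 3 = 61.5, so 62 (stated 60; a noncentral t calculation gives 58).
- n=246, r=.20: power = Φ(atanh(.20)·√243 − 1.960) = Φ(3.160 − 1.960) = 88.5% (stated 90%). The r detectable with 90% power is .205.

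The stated figures are reproduced to within rounding and choice of approximation.

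**Step 2: the same sample under Bonferroni**, with each test at .05/m.

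- m=3: Φ(3.160 − 2.394) = 77.8%.
- m=6: Φ(3.160 − 2.638) = 69.9%.

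**Step 3: why Holm dominates.** Order the p-values and compare the k-th smallest with .05/(m − k + 1), stopping at the first failure. Every threshold is at least .05/m, so each Bonferroni rejection is also a Holm rejection. Suppose m₀ hypotheses are true nulls. The first of them to be rejected must have p ≤ .05/m₀, and the union bound over m₀ nulls gives a family-wise error of at most .05 under any dependence.

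**Step 4: size of the gain.** Simulation with 200,000 replicates, n=246, r=.20 for each real effect, correlation .5:

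| Family | Real effects | Average power, Bonferroni → Holm | All real effects found, Bonferroni → Holm |
|---|---|---|---|
| 3 | 1 | 77.8% → 77.9% | 77.8% → 77.9% |
| 3 | 2 | 77.8% → 80.7% | 65.8% → 71.4% |
| 3 | 3 | 77.9% → 84.7% | 57.9% → 74.1% |
| 6 | 1 | 69.8% → 69.8% | 69.8% → 69.8% |
| 6 | 3 | 69.8% → 72.7% | 46.7% → 52.9% |
| 6 | 6 | 69.9% → 80.0% | 33.1% → 61.2% |

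The chance of finding at least one real effect hardly moves (94.2% under both rules with three of three real; 95.6% under both with six of six). Simulated family-wise error under Holm was at most .050 in every scenario. Holm rejected everything Bonferroni rejected in every replicate.

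**The case against.** Bonferroni is valid, and nothing in the sentence is wrong or self-contradictory. Choosing between two valid procedures and defining families could be left to an analysis plan. That largely stands: this is a question of efficiency. It remains a fair point because the protocol does not leave the choice open; it names the procedure.

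The size also depends on the scenario. Hypothesis 3i expects domain-specific delays, so a family in which every effect is real is not the natural case. With half of six effects real the gain in average power is about 3 points, and with one it is nil. This stands, and the all-real rows above should be read as the upper end.

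A reader might infer four stronger things that the protocol does not support:

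- **That Bonferroni governs all WP3 testing.** The permutation and threshold-free cluster enhancement rules cover other analyses. The phrase about neuroimaging analyses could even be stretched over ROI and tract summaries, though those methods fit maps and not single regression coefficients.
- **That Bonferroni contradicts a stated aim of limiting type 2 error.** That aim belongs to the sentence on neuroimaging analyses and the methods named there.
- **That correlated measures strengthen the case for Holm.** The protocol states no correlation and Holm does not use it. With six of six real, Holm's average power is 82.6% for independent tests and 80.0% at correlation .5.
- **That missed effects will distort the domain question.** No calculation here shows this.

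**Conclusion.** For the WP3 families of regressions on summary measures, plain Bonferroni is a valid choice that Holm dominates for testing. At n=246, r=.20 and correlation .5, Holm adds between 0 and about 7 points of average power in a family of three (84.7 − 77.9 = 6.8) and between 0 and about 10 points in a family of six (80.0 − 69.9 = 10.1). The chance of finding every real effect rises by up to about 16 points (57.9% to 74.1%) and 28 points (33.1% to 61.2%) respectively, but only when all effects are real. Nothing is gained when one effect is real, and Holm does not restore the unadjusted 88.5%.

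That Holm never does worse rests on no assumption. The sizes rest on assumed family size, number and equality of real effects, and correlation. Type 1 error control is not in question.

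**What to change.** Replace the Bonferroni sentence in section 9.2 (WP3) with wording such as: *Within each family of WP3 regression tests, the Holm step-down procedure will hold the family-wise error rate at 5%, and adjusted p-values will be reported.*

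The cost is one sentence and a trivial change in the analysis code, with no effect on data collection, sample size or error rate. The one drawback is that simultaneous confidence intervals matching Holm are less simple than Bonferroni intervals. The change should be made before WP3 results are analysed.
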